**D.4d. Quantitative evaluation:**

**D.4d1. Cohort identification:** To assess impact of IF efforts, we will identify a cohort of at-risk patients—those who have OUD but are not prescribed MOUD—to track their outcomes over time. Methods to identify at-risk patients will be harmonized across all implementation sites. These will include use of available data in the Corporate Data Warehouse (CDW), including medication/pharmacy records (inpatient and outpatient), toxicology screen results, primary care and mental health care utilization, inpatient admissions, comorbidity data, recent treatment and service use such as alternative pain treatments for the subgroup of MOUD patients with pain, and other information to determine at-risk Veterans appropriate for referral for MOUD. We will compare outcomes at each implementation site during the post-implementation period to outcomes prior to implementation, using each site as their own control. Each site will have a defined implementation start date and an implementation start-up period of 3-months in which outcomes will not be attributed to either the pre- or post-implementation period. For sites that have booster or additional implementation efforts, additional start dates of those efforts will be tracked. Harmonization of definitions for at-risk Veterans will also facilitate comparing sites across VHA not participating in MOUD-related implementation activities to examine secular trends and to rapidly identify targets for expanding the implementation efforts for MOUD referral in additional VISNs. A person-years approach will be used as Veterans may be at-risk and eligible for referral for MOUD at multiple time points during the three-year project.

**D.4d2. Implementation/clinical outcomes:** The Quantitative/Economic Core will work with the Implementation Core on two primary areas: (1) ensuring accuracy and consistency of assessments of RE-AIM

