**D.5f. Downstream/concurrent costs:** Recent literature has found the additional treatment costs of MOUD are offset by lower utilization of medical services. To calculate the cost offsets associated with MOUD in VHA, we will conduct an ancillary analysis of the cost trajectories between patients treated with and without MOUD. This will be a national analysis to ensure high numbers of MOUD recipients. We will first identify national sample of Veterans eligible for MOUD and the subgroup of those treated with MOUD in 2018. We will extract each patient's healthcare costs using inpatient, outpatient, and pharmacy utilization between 2016 to 2019, which will be used to develop of longitudinal cost trajectories similar to prior work led by Drs. [name] and [name] in the areas of complementary and integrative health. To identify the cost or cost savings attributable to initiation of MOUD, we will compare the costs over time for those patients that are treated with MOUD to those patients that are not treated with MOUD using a difference in differences specification. A generalized gamma regression with log link will be specified. Personnel from HERC are included in the Quantitative/Econ Core to help identify all relevant clinical care costs, as well as to assist in capture all potential utilization activities delivered through community care activities.

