## **G. Management plan and timeline**

**G.1. Management plan:** [name] will serve as corresponding PI and will lead the CONDUIT Coordinating Center, responsible for overseeing and ensuring integrated, productive interactions among the Cores and among the Cores and the implementation sites. [name] will lead the Veteran Engagement Core. He will be responsible for coordination of recruitment, orientation and prospective administrative support for this group. He will ensure collaboration and alignment with other ongoing Veteran engagement initiatives. [name] will lead the Implementation Core and has extensive experience working as an implementation scientist and leading implementation work across multiple projects. Drs. [name] and [name] will lead the Quantitative /Economic Core. [name] will be responsible for working with the Implementation Core to identify direct analytic support needs. He will oversee analytic staff who will extract and clean data from CDW and REDCap. [name] will oversee economic activities including calculating the cost of implementation efforts, estimating the potential cost savings of initiation of MOUD, and calculating the return on investment of each project.

In the first six months of the project, there will be at least bi-weekly phone meetings for among the Core leads and [name] to ensure coordination across External Facilitation teams (**Table 7**). After six months, these meetings will transition to monthly meetings unless more frequent meetings are necessary. There will also be regular email and telephone contact. The Implementation and Quantitative/ Economics Core will meet weekly with their respective teams. Our operational partners will serve as our Strategic Advisory Group, including 1 to 2 Veterans from the CONDUIT VEB. They will guide the consortium with respect to VHA priorities. There will be a monthly CONDUIT-wide teleconference for all project personnel. Twice annually, the project-wide meeting will include the Strategic Advisory Group. See the Multiple PI Plan for further details about the organization, responsibilities and plans for integration of implementation efforts across the EF teams .

**G.2. Deliverables:** In Phase 2 of this Partnered Implementation Initiative, CONDUIT will build on Phase 1 deliverables to generate several products that will advance OUD care more broadly in VA.

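### The D.5f cost analysis targets the effect of starting MOUD but selects anyone treated in 2018, so Veterans already on MOUD enter with a treated baseline

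*Combined protocol and SAP*

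**What the plan says.** D.5f (Downstream/concurrent costs) sets out a national analysis of cost trajectories in patients treated and not treated with MOUD.

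- **Target:** "To identify the cost or cost savings attributable to initiation of MOUD". Section G.1 describes the same task as "estimating the potential cost savings of initiation of MOUD".
- **Cohort:** "We will first identify national sample of Veterans eligible for MOUD and the subgroup of those treated with MOUD in 2018".
- **Cost window:** "We will extract each patient's healthcare costs using inpatient, outpatient, and pharmacy utilization between 2016 to 2019".
- **Contrast:** treated patients against "those patients that are not treated with MOUD using a difference in differences specification".
- **Model:** "A generalized gamma regression with log link will be specified", so the effect is a ratio of costs.

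D.5f does not define eligibility for MOUD. It gives no index date and no cut between before and after. It does not say how a comparison patient treated in 2016-2017 or in 2019 is classified. D.5b says that return on investment will include downstream and concurrent care costs.

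**The concern.** The target is the effect of starting treatment, while the cohort is defined by being on treatment at some time in 2018. Two Veterans show the difference. One has a first fill in June 2018: the earlier period is untreated and the later one treated, as the contrast needs. The other has filled continuously since 2015 and meets the same rule, but was on MOUD both before and after. That Veteran's change in cost says nothing about starting MOUD, yet is averaged into the treated group's change. A similar problem arises if the comparison group contains Veterans who were on MOUD in 2016-2017 and had stopped by 2018, because their before-period is treated too.

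At stake is the cost-offset figure for MOUD, and through it the return on investment that Aim 3 offers VISN leadership for decisions on adoption, scale and spread.

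**Working it through.** The plan gives no effect size, sample size or prior-user share for this analysis, so it has no figure to reproduce. The check is to follow the rule as written and see what the contrast would estimate.

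**Inputs from the documents:** treated group defined by any treatment in 2018; costs for 2016-2019; difference in differences with a log link.

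**Assumptions:** before is 2016-2017 and after is 2018-2019; parallel trends, with costs rising 3% a year on the log scale; initiators on treatment throughout 2018-2019; prior users and initiators with the same underlying untreated cost; *p*, the share of the treated group already on MOUD, at 0%, 25%, 50% and 75%; true cost ratio *r* for being on MOUD of 0.80 (a 20% saving), with 1.20 as a check.

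**Formula.** With a saturated log-link model, the estimate is (treated after ÷ treated before) ÷ (comparison after ÷ comparison before). If prior users have been on MOUD since before 2016 and the effect is constant, the trend cancels and

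estimated ratio = r ÷ [(1 − p) + p·r]

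| p | r = 0.80 | Estimate | r = 1.20 | Estimate |
|---|---|---|---|---|
| 0% | 0.80/1.00 | −20.0% | 1.20/1.00 | +20.0% |
| 25% | 0.80/0.95 | −15.8% | 1.20/1.05 | +14.3% |
| 50% | 0.80/0.90 | −11.1% | 1.20/1.10 | +9.1% |
| 75% | 0.80/0.85 | −5.9% | 1.20/1.15 | +4.3% |

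If prior users instead started in January 2017, only about half of their baseline is treated. The true −20% is then estimated as −17.9%, −15.7% and −13.4% at p = 25%, 50% and 75%. All of these move toward zero.

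**Is the direction guaranteed?** No. The same cost ratio was computed with effects that change over time on MOUD, for prior users who started in 2016:

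| Effect on log cost by year on MOUD | Initiators only | p = 25% | p = 50% | p = 75% |
|---|---|---|---|---|
| −0.1, −0.2, −0.3, −0.4 | −13.9% | −14.8% | −15.8% | −16.9% |
| +0.2, 0, −0.2, −0.3 | +10.9% | −0.1% | −10.5% | −20.3% |

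The first row moves away from zero and the second changes sign.

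**Comparison group.** If a share *c* of comparators was treated only in 2016-2017 and the effect is constant, the estimated ratio is 0.80 × (1 − 0.2c). This gives 0.784 (−21.6%) at c = 10% and 0.768 (−23.2%) at c = 20%, again away from zero.

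**Are there prior users?** Table 1 (Section C.1) counts Veterans on MOUD in four VISNs: 2,117 + 833 + 1,554 + 485 = 4,989 in Q2 FY18, and 2,216 + 863 + 1,701 + 538 = 5,318 a year later. So a substantial group was already on MOUD early in 2018. The table does not say how many of them were treated in 2016-2017.

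**The case against.** **Eligibility may already exclude current users.** D.4d1 defines the at-risk cohort as "those who have OUD but are not prescribed MOUD", and D.5f draws its sample from Veterans eligible for MOUD. If the authors meant that definition, much of the problem goes away. But it is written for Aim 2, D.5f does not cite it, and D.5f sets no date at which being untreated would be assessed. The possibility is fair; the text does not establish it.

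**The bias cannot be signed.** A reader might infer that the plan necessarily understates the cost offset. That needs an immediate, constant effect. D.5f itself plans longitudinal trajectories, so an effect that varies with time on MOUD is plausible, and earlier treatment among comparators pushes the other way. This objection stands.

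**The size cannot be derived from Table 1.** A reader might turn the growth from 4,989 to 5,318 into a prior-user share and hence a percentage bias. A net rise of 329 is compatible with low or high turnover, and the documents give no exit rates or treatment durations. The table also covers four VISNs in single quarters, whereas D.5f is national. This objection stands too.

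**The analysis is ancillary.** D.5f calls it so. The primary economic outcome in D.5b, cost per additional Veteran initiating MOUD, is built from implementation and program-delivery costs, and D.5g plans separate cost models. A reader might infer that the primary economic result is compromised; the documents do not support that. Return on investment is still affected.

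**Conclusion.** The mismatch holds. Followed as written, D.5f mixes Veterans starting MOUD in 2018 with Veterans already on it, and the difference in differences does not estimate the effect of initiation. This is a stated selection rule that disagrees with its stated target.

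Direction and size are conditional. Under an immediate, constant effect the estimate is attenuated: a true −20% appears as about −16%, −11% or −6% for assumed long-standing prior-user shares of 25%, 50% and 75%. Under an effect that varies with time on MOUD, or with previously treated comparators, it can be exaggerated or reversed. The actual prior-user share is not in the documents, so these figures are illustrations and not bounds. Because the sign is uncertain, the error could not be corrected afterwards by a simple scaling.

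It should be fixed, but it is not critical: the result feeds return on investment and leaves the primary economic outcome untouched.

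**What to change.** Amend D.5f as follows.

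1. Define the treated group as Veterans whose first MOUD fill or administration after a stated MOUD-free look-back falls in 2018. No MOUD in 2016-2017 is one choice. Shorter look-backs that admit Veterans restarting treatment can be a sensitivity analysis.
2. Anchor before and after to that first date. Any index date in 2018 leaves at least two years of cost data before it and at least one after. Anchoring also removes a separate dilution: with a calendar-year cut, Veterans starting evenly through 2018 would be treated for only (0.5 + 1) ÷ 2 = 75% of 2018-2019, even with no prior users.
3. Apply the same look-back to comparators and give each a matched 2018 index date.
4. State how comparators who start MOUD after their index date, including in 2019, are handled, for example by censoring at the start.
5. Keep the version with everyone treated in 2018 as a sensitivity analysis.
6. If eligibility was meant to carry the D.4d1 at-risk definition, say so and give the date at which it is assessed.

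The cost is new wording, a filter on the 2016-2019 window already planned, and the matching of index dates. The treated group will be smaller, by an amount the documents do not allow one to calculate, although the sample is national and was chosen to give many MOUD recipients. The result will apply to new starts and not to all Veterans on MOUD, and the report should say so.

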## **D. Approach**

**D.1. Overview:** CONDUIT’s overall objective is three-fold: 1) increasing uptake of evidence-based MOUD (specifically buprenorphine formulations FDA-approved for OUD and injectable naltrexone) across 4 distinct clinical settings using IF strategies; 2) evaluating the effectiveness of those strategies across highly-salient metrics of implementation success and 3) estimating costs of implementation activities. CONDUIT uses evidence-based IF consisting of 4 EF teams partnering with internal facilitation teams at 57 sites across 6 VISNs to implement evidence-based practices across the OUD/pain continuum of care. Three Cores – Veteran Engagement, Implementation, and Quantitative/ Economic – will work across teams and sites to ensure alignment of measures and to support cross-CONDUIT deliverables.

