Each of the EF teams will work collaboratively with internal facilitation teams to deploy the core IF activities outlined in Table 3 as well as additional IF activities noted. Evaluations performed by the Implementation Core, in partnership with each facilitation team (e.g., formative evaluation, survey, IF logs as outlined in D4 below), will identify whether any adaptations need to be made to the IF activities. For example, if the Telehealth EF team identifies technical issues as a barrier to implementation, they will incorporate technical assistance into IF, and it will be added to their IF log for tracking its use during implementation.

**D.3d. Integration of implementation activities:** The foundation of CONDUIT's implementation activities are the structured interactions between the four EF teams and internal facilitation teams. A core set of IF activities will be used across all facilitation teams, and EF teams will use additional ones based on the needs of their sites or clinical settings (**Table 3**). EF and internal

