**D.4d3. Analytic approaches:** Our non-randomized evaluation design is necessary because randomization was not possible due to our partnership with VISN leadership and outreach efforts for individual site participation. A key goal is to demonstrate to VISN and facility leadership the value of implementation; therefore, we will estimate implementation outcomes for each of our individual sites and pool implementation sites as appropriate. This will allow us to provide descriptive quantitative information about individual implementation efforts to be combined with qualitative findings about implementation success. Although these analyses will allow for some comparison of effectiveness across individual team efforts, we do not propose formal direct comparisons of teams. There are several statistical limitations to the non-randomized evaluation design that we will address through pragmatic approaches. To account for secular trends in increased use of MOUD that may not be due to our implementation efforts, we will track other related implementation efforts such as initiation of additional SCOUTT efforts, and monitor national dashboards to generate a secular rate among non-intervention sites. We will use this secular rate and test to determine if CONDUIT activities increase use of MOUD above this rate, rather than a null hypothesis of 0. Because we are calculating outcomes for each of the individual sites, the risk of a spurious finding due to multiple testing is possible. We will use caution when interpreting any moderate p-values (e.g. 0.01 to 0.05) as significant. For ease in reporting to VISN and site leadership, we will utilize direct pre- and post-implementation period comparisons. Additional multivariate adjusted analysis using time-to-event semi-parametric methods will also be explored. These models will focus on initiation of MOUD treatment, and will allow for examining clinical and demographic characteristics, including time from initial OUD diagnosis.

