**D.5g. Implementation, clinical and cost outcomes analysis:** We will aggregate the personnel time and financial resource data collected to calculate the total cost of IF for each implementation effort. Using an "intent-to-treat" approach with person-years as the unit of analysis, we will calculate separate multilevel mixed models for each clinical/RE-AIM outcome and cost outcome. We will pool implementation efforts across clinical settings as appropriate (e.g. all primary care implementation efforts will be combined into a single analysis). Exposure to IF implementation-as-usual conditions will be based on timing and randomized as appropriate to each project, such as stepped-wedge designs. We will account for clustering of patients across multiple exposure periods, as well as nesting of patients within clinical settings. This approach will allow assignment of at-risk Veterans to different facilitation levels as well as control for secular trends in pre-post implementation efforts. At-risk Veterans who were initially exposed to implementation-as-usual condition will be censored relative to outcome assessment for that phase if they or their provider is exposed to IF. The model will include an indicator variable for implementation and clinic program status, and an interaction between time and this indicator variable to assess for the independent effect of implementation separate of secular trends. Longer term costs, such as 12-month medical care cost trajectories following exposure to potential referral to MOUD will be included as appropriate. Markov models based on the outcome of the point estimates from the clinical and economic outcome models will be developed to estimate confidence intervals of key measures such as cost per additional at-risk patient receiving MOUD.

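### The pooled mixed model names no site, health-system or site-by-period term although facilitation starts by site, so its standard errors are likely to be too small under staggered starts or site-varying change

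*Combined protocol and SAP*

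**What the plan says.** Section D.5g sets out the pooled analysis: "we will calculate separate multilevel mixed models for each clinical/RE-AIM outcome and cost outcome". The correlation it allows for is given in one sentence: "We will account for clustering of patients across multiple exposure periods, as well as nesting of patients within clinical settings". The fixed part is also brief: "The model will include an indicator variable for implementation and clinic program status, and an interaction between time and this indicator variable". Efforts are to be pooled where appropriate, with the example that "all primary care implementation efforts will be combined into a single analysis". On exposure, "Exposure to IF implementation-as-usual conditions will be based on timing and randomized as appropriate to each project, such as stepped-wedge designs".

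Elsewhere in the protocol:

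- D.1 counts the settings: "across 4 distinct clinical settings using IF strategies". The D.3 summaries by setting list primary, specialty, acute and telehealth care.
- D.3d treats sites and settings as different things: "EF teams will use additional ones based on the needs of their sites or clinical settings".
- D.4d1 gives each site its own start date and compares each site with itself before and after.
- D.4d3 adds that "we will estimate implementation outcomes for each of our individual sites and pool implementation sites as appropriate".
- D.3c and Table 2 list 57 sites (24 medical centers and 33 CBOCs) in 29 health-system rows.

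No part of the quantitative plan names a random or fixed effect for site, health system or site-by-period.

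**The concern.** Facilitation is delivered to a site and begins on a date set for that site. Veterans at one site share staff, prescribers, leadership and local events. In a pooled analysis the information about a facilitation effect therefore comes largely from how many sites changed and how consistently, and less from how many Veterans were counted.

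If clinical settings means the four care types, the stated nesting does not capture this. In the plan's own all-primary-care example it has a single level and absorbs nothing. Differences between sites, and differences between sites in how much they change, would then be treated as independent patient-level noise.

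At stake are the pooled effect intervals, the pooled test against the secular rate (D.4d3), and the intervals for cost per additional patient, which D.5g derives from these models. D.5a and G.4 say the results will inform decisions on scale, spread and national expansion, so inference is meant to reach beyond the participating sites.

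**Working it through.** **1. Does the power section already allow for clustering?** Table 6 gives detectable effects of 0.40, 0.32, 0.20 and 0.10 for 50, 75, 200 and 750 Veterans at 80% power. Assuming a two-sided 5% test (Table 6 states no alpha), a one-sample formula for independent patients, d = (1.960 + 0.842)/√n, gives 0.396, 0.323, 0.198 and 0.102. These match after rounding. Table 6 therefore has no design effect, and nothing there makes up for D.5g.

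**2. Is between-site correlation negligible?** The 29 MOUD rates in Table 2 run from 8.5% to 40.3%, with unweighted mean 23.3% and SD 8.9 points. A crude between-system ICC is 0.0887²/(0.2333 × 0.7667) ≈ 0.044. It is cross-sectional and at system level, but it makes an assumed ICC range of 0.01 to 0.05 reasonable.

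**3. Balanced pre/post, each site in both periods.** With m Veterans per site-period and cluster autocorrelation CAC (how far a site's effect persists from one period to the next), the ratio of true SE to SE without a site term is √[(1 − ICC) + m × ICC × (1 − CAC)].

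- CAC = 1 (stable site effects): ratio 0.975 to 0.995. The SE is not understated.
- CAC 0.5 to 0.9, m 13 to 200: ratio 1.00 to 2.44, actual size of a nominal 5% test 5% to 42%.

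**4. Staggered starts.** A null simulation used 57 sites, 6 periods, setting and period effects but no site term, 5 to 35 patients per site-period, ICC 0.01 to 0.05 and CAC 0.8 to 1.0. The ratio was 1.05 to 2.3 and the size about 6% to 42%. The outcome was continuous, with 400 runs per cell (Monte Carlo error about 1 to 2.5 points). Here the SE is understated even with stable site effects, because exposed and unexposed periods are partly compared across sites.

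**5. Does change vary by site?** Table 1 changes, Q2 FY18 to Q2 FY19, in points: 1, 24, 7, −1, 4, 12, 5, 5. Implied denominators are count/rate, and the mean sampling variance of a change is about 7.

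- All eight: variance 61.6, SD 7.8; beyond sampling error √(61.6 − 7.1) ≈ 7.4.
- Without Manchester, whose implied denominator falls from 153/0.22 ≈ 695 to 139/0.46 ≈ 302: variance 17.6, SD 4.2; beyond sampling error √(17.6 − 6.6) ≈ 3.3.

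These motivate a range of 3.5 to 7.5 points for the between-site SD of change, τ.

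**6. Illustration.** Inputs: p = 23.7% (national rate, Table 2), 57 sites, n Veterans per site-period (assumed), K clusters carrying the variation.

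- Patient-only SE = √[2 × 0.237 × 0.763/(57n)]: 0.56 points at n = 200, 1.13 at n = 50.
- SE with site variation = √(SE² + τ²/K).
- Size = 2 × (1 − Φ(1.96/ratio)), where ratio is the second SE over the first.

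| n | K | τ | SE with variation | Ratio | Size |
|---|---|---|---|---|---|
| 50 | 57 | 3.5 | 1.22 | 1.08 | 7% |
| 50 | 57 | 7.5 | 1.50 | 1.33 | 14% |
| 200 | 57 | 3.5 | 0.73 | 1.30 | 13% |
| 200 | 57 | 7.5 | 1.14 | 2.03 | 33% |
| 200 | 29 | 3.5 | 0.86 | 1.53 | 20% |
| 200 | 29 | 7.5 | 1.50 | 2.67 | 46% |

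**The case against.** **The phrase is ambiguous.** D.2 (Veteran Engagement Core) and D.4c use clinical setting for a local unit. The D.5g pooling sentence can be read the same way, since combining all primary care efforts means pooling over local clinics within one care type. This stands: the four-type reading is the best supported but not the only one. It does not close the gap, because a local-unit intercept still leaves out site-by-period variation and the health system that several CBOCs share.

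**Each site is its own control.** With balanced periods and stable site effects, site differences cancel (step 3). This stands and limits the point. A reader might infer that every pooled standard error in the plan is too small, and the documents do not support that. The risk is specific to timing-based or stepped exposure, which D.5g foresees, and to change that varies by site.

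**The sizes are soft.** A reader might take 33% or 46% as the expected false-positive rate. The documents do not support that either:

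- Table 1 and the 23.7% are shares of patients on MOUD. Reach is initiation among at-risk Veterans not on MOUD, in person-years.
- All eight Table 1 facilities received Phase 1 facilitation, so their spread is partly real differences in effect and not pure null variation.
- The upper end of τ rests on one anomalous row. With seven facilities, a normal-theory 95% interval for the excess SD is about 0.8 to 8.9 points, so 3.5 is not a lower bound.
- The plan gives no number of Veterans per site-period, D.4d4 warns of small facilities, and 33 of the 57 sites are CBOCs.
- The calculation is a two-period difference, whereas D.5g tests an interaction with time.

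All of this stands. It makes the figures illustrative without removing the direction of the error.

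**Conclusion.** The point holds in a conditional form. D.5g states a specific correlation structure, and that structure omits the level at which facilitation starts. Fitted as written, the model is likely to understate uncertainty under staggered or stepped starts, or where the pre/post change differs between sites.

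Over the assumed ranges, the actual size of a nominal 5% test could be anywhere from barely above 5% to several times that. The main drivers are Veterans per site-period and the spread of change between sites, and the documents fix neither. The 29-system figures assume that all of the variation sits at system level. The plan should be changed because the omission is clear and cheap to correct, whatever the exact error rate.

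**What to change.** In D.5g, define clinical setting and replace the nesting clause with wording such as:

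> Models will include random intercepts for site, nested within health system where estimable, and a random site-by-period (site-specific implementation) effect, in addition to correlation among repeated periods for the same Veteran. Clinical setting will be a fixed factor only in analyses that span more than one setting.

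For pooled pre/post comparisons (D.4d3), state that standard errors will be clustered by health system (robust variance or cluster bootstrap), with a small-sample correction when clusters are few. State also how the random structure will be simplified if a single-setting analysis has too few sites to estimate every term.

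The cost is model wording and wider intervals. No new data are needed beyond site and health-system identifiers.
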